1. INTRODUCTION

1.1 Background and rationale

Orthostatic hypotension (OH) is a common and disabling condition characterised by a significant reduction in blood pressure (BP) on standing upright, typically causing dizziness and falls.

There is little good quality evidence to support the management of OH. First line treatment is usually lifestyle advice and non-drug therapies. Where these are not effective there are two pharmacological options, fludrocortisone and midodrine; however, there is a lack of robust evidence on the clinical and cost-effectiveness of these treatment strategies and long-term efficacy and safety is unclear.

The CONFORM-OH trial, commissioned by NIHR HTA, was designed to evaluate the clinical and costeffectiveness of fludrocortisone and midodrine for the management of symptomatic OH in comparison with conservative management (lifestyle advice and non-drug therapies).

The trial included a 10-month internal pilot phase to assess recruitment and retention with defined progression criteria. At a meeting of the Trial Steering Committee (TSC) on 30th August 2022, nine months into the internal pilot phase, it was agreed the that the trial should close to recruitment on the basis of very low recruitment rates.

This statistical analysis plan describes the trial design, outcome measures and plans to descriptively summarise available data. Details of analyses which would have been performed, had the trial continued to full enrolment, are described in an Appendix.

1.2 Objectives

This trial was designed to evaluate the clinical and cost-effectiveness of three different treatment strategies for the management of symptomatic OH:

- I. Control: Conservative management (lifestyle advice and non-drug therapies)
- II. Conservative management plus fludrocortisone
- III. Conservative management plus midodrine

1.2.1 Primary objective

To determine whether the treatment strategies of conservative management plus fludrocortisone, and conservative management plus midodrine, improve symptoms of OH compared to conservative management alone, as measured by change in the Orthostatic Hypotension Questionnaire (OHQ) score at six months.

1.2.2 Secondary objectives

To determine how the treatment strategies of conservative management plus fludrocortisone, and conservative management plus midodrine, affect the following outcomes compared to conservative management alone over a 12-month period:

- 1. Activities of daily living (ADLs) measured by the Nottingham Extended ADL (NEADL) scale
- 2. Falls and syncope (number of falls, number of fallers/non-fallers, fall rate per person year, time to first fall, fall-related injuries, number of syncopal events)
- 3. Standing blood pressure and postural blood pressure drop
- 4. Side effects and the safety data associated with each treatment strategy
- 5. Health-related quality of life measured by the EQ-5D-5L
- 6. Quality adjusted life years (QALYs) estimated from responses to the EQ-5D-5L and data derived from the literature
- 7. Costs to the NHS, personal social services and patients
- 8. Cost-effectiveness of each treatment strategy modelled from a patient and NHS and personal social services perspective measured in terms of the incremental costs per QALY gained

Objectives 5-8 are outside the scope of this analysis plan and will be covered in the Health Economics Analysis Plan.

1.2.3 Exploratory objectives

An exploratory objective was to compare the clinical effectiveness (measured by change in the OHQ score at six months) of fludrocortisone with midodrine.

2. STUDY METHODS

2.1 Trial design

CONFORM-OH is a pragmatic, multi-arm, multi-stage, parallel group, prospective, randomised, open label, superiority trial. The trial was designed to assess the effectiveness of two drug therapies to improve the symptoms of OH compared to conservative management.

Adult patients presenting with symptomatic OH refractory to lifestyle modification were allocated (1:1:1) to receive either conservative management alone, conservative management plus fludrocortisone or conservative management plus midodrine for a period of 12 months.

The primary outcome is assessed after a period of 6 months. This timing was chosen based on a number of factors, including patient consultation, allowing adequate time for dose titration, and balancing adequate exposure with likely adherence and retention rates. Longer term follow-up will continue to 12 months.

An interim analysis, based on available three- and six-month primary outcome data, was planned to take place after the 200th patient had been recruited. If an intervention arm showed no benefit compared to the control arm (see Appendix for further details) it would be recommended to be dropped from the study, with control (conservative management) and the alternative intervention arm continuing to the planned recruitment target of 366 participants in a 1:1 ratio. If both intervention arms showed lack of benefit, the study would be recommended to stop. Recruitment would continue to all three arms while the interim analysis was being conducted.

The trial also included a 10-month internal pilot phase to assess recruitment and retention rates.

2.2 Study setting and patient population

Adult patients with symptomatic OH refractory to a minimum of 4 weeks of lifestyle modification were recruited. Patients were to be recruited from approximately 20 NHS trusts across the UK, typically from secondary care settings such as falls clinics, day hospitals, geriatric medicine clinics and movement disorder clinics.

For a full list of inclusion and exclusion criteria refer to section 4 of the study protocol.

2.3 Randomisation and blinding

Participants were allocated in a 1:1:1 ratio to receive conservative management alone, conservative management plus fludrocortisone or conservative management plus midodrine. A minimisation algorithm with a random element was used to assign treatment allocation. Minimisation factors were age (≥80 vs <80 years), aetiology (neurogenic vs non-neurogenic OH) and recruiting site/centre (to account for possible difference in usual care practice).

The minimisation system was provided by SealedEnvelope[™] as a 24-hour, central, secure, web-based system accessed by delegated members of the research team at each site to perform randomisation.

The minimisation algorithm incorporates a random element such that there is an 80% chance the participant is allocated to the arm which minimises imbalance, with the remaining arms chosen with 10% probability each. In the case of ties, one of the tied arms is chosen at random to be the 'preferred' arm and assigned an 80% probability of being chosen with the remaining arms assigned a 10% probability each.

This is an open-label trial and there will be no blinding of participants, clinicians or research staff. It was planned that the trial statistician would not have access to outcome data by treatment group until the end of the trial. The interim analysis and closed reports to the Data Monitoring Committee (DMC), i.e. containing data presented by randomised treatment group, would have been performed/prepared by a statistician (a member of the Biostatistics Research Group) not otherwise involved in the study and reviewed by the Lead Statistician. However, following the decision to close the trial early it was agreed the trial statistician no longer needed to remain blinded. The perceived risk of having an unblinded statistician in an otherwise open-label trial was deemed to be minimal given that data would only be summarised descriptively and no interim or final inferential analyses would be performed.

2.4 Definition of outcome measures

2.4.1 Primary endpoint

The Orthostatic Hypotension Questionnaire (OHQ) [1] is completed at baseline, three, six and 12 month follow-up. The primary endpoint is the overall composite OHQ score at six months. The OHQ is validated for use in both clinical and research settings [2] and will be scored according to the validated scoring method [1].

The OHQ is composed of two sections: the first section consists of six questions, which rate the severity of six different symptoms on a scale of 0 to 10 (Orthostatic Hypotension Symptom Assessment Scale – OHSAS). The second section is composed of four questions, which rate the impact of symptoms on standing and walking (Orthostatic Hypotension Daily Activity Scale – OHDAS). The questions on the OHDAS are scored on a scale of 0 to 10 but also include an option of 'cannot be done for other reasons'.

The OHSAS score is calculated by averaging the responses to the six questions on the OHSAS. Similarly, the OHDAS score is calculated by averaging responses to the four questions on the OHDAS. Items which are scored as zero or answered 'cannot be done for other reasons' at baseline are not included in the scoring. Post-baseline scores are calculated using only those items which were included in the baseline score. If any item on the OHDAS which was included in the baseline score is missing or answered 'cannot do for other reasons' at a post-baseline assessment a value will be assigned using last observation carried forward.

An overall composite OHQ score will be calculated by averaging the OHSAS score and the OHDAS score. This score takes a value between 0-10, with higher scores indicating worse symptoms / interference.

At each follow-up time point the change from baseline will also be calculated as the follow-up score minus the baseline score.

2.4.2 Secondary endpoints

Activities of daily living (ADLs) measured by the Nottingham Extended ADL scale

The Nottingham Extended ADL (NEADL) scale is a 22 item questionnaire designed to assess the level of independence in carrying out social and domestic activities [3]. There are four sections/subscales which are mobility (six items), kitchen (five items), domestic (five items) and leisure (six items). Each item is scored as "on my own"; "own my own with difficulty"; "with help"; and "not at all/no".

When no more than 2 items are missing within subscales we will use simple imputation methods by replacing the missing item with the median response from the respondent specific completed questions within the subscale. This is can provide a valid approach for psychometrically validated questionnaires where responses to items within subscales are correlated [4]. A similar approach has also been used in other randomised controlled trials involving the NEADL scale [5].

One point is awarded per item if the participant selects either "on my own" or "on my own with difficulty." A score of zero is awarded if the participants selects "with help" or "not at all/no". All items are then summed to give an overall NEADL score which ranges from 0 - 22. Higher scores indicate greater independence. The score will not be calculated if any items are missing, after using the imputation method described above. The NEADL

questionnaire is measured at baseline, three, six and 12 month follow-up. At each follow-up time point the change from baseline will also be calculated as the follow-up score minus the baseline score.

Falls and syncope (number of falls, number of fallers/non-fallers, fall rate per person year, time to first fall, fall-related injuries, number of syncopal events)

Falls and faints (syncopal events) are self-reported by the participant and collected in monthly falls diaries which should be returned at three, six and 12 month follow up time points.

The number of falls for each participant will be summed over the 12 month period. The fall rate per person year will be calculated in each arm as the total number of falls from all participants in that arm divided by the total observation time for all participants in that arm. For each participant their observation time will be measured as the time (in years) from randomisation to the date of the last completed fall diary.

Participants will be classed as fallers if they report at least one fall over the 12 month period and a non-faller if they did not report a fall and returned at least one fall diary; i.e. participants who do not return at least one fall diary will be excluded from the analysis. We will also categorise participants as a single faller if they fall once, a recurrent faller if they fall twice or more, and a non-faller if they do not report any falls.

The number of faints (syncopal events) for each participant will be summed over the 12 month period. The syncopal event rate will be calculated as described above. In addition, we will report the total number, and rate of, a combined outcome of fall and faints.

Time to first fall will be measured as the time from randomisation to the first reported fall.

Fall related injuries are reported as free-text fields. There will be a medical review of any coding of free-text fields required.

Standing blood pressure and postural blood pressure drop

The lowest (nadir) standing blood pressure (systolic and diastolic) is measured at baseline, three, six and 12 month follow-up.

Blood pressure will also be measured in the supine position (lying down) at baseline, three, six and 12 month follow-up.

Postural blood pressure drop will be defined as (supine – lowest standing blood pressure) for systolic and diastolic measurements at each time point.

For each measurement the change from baseline will also be calculated as the follow-up value minus the baseline value.

Hospital admissions

Hospital admissions during the 12 month trial period will be collected from medical records. The number of admissions per participant will be calculated.

Reasons for admission will be tabulated. 'Other' reasons will be coded/grouped where possible with a medical review of any coding.

The rate of hospital admissions per person year will be calculated in each arm as the total number of admissions from all participants in that arm divided by the total observation time for all participants in that arm. For each participant their observation time will be measured as the time (in years) from randomisation to their last completed follow-up visit.

Side effects and the safety data associated with each treatment strategy

Adverse Events (AEs) will be collected over the 12-month trial period. At each follow-up visit participants will be asked about any side effects or adverse events they have experienced. This will be by open-ended questioning rather than a review of specific side effects or symptoms. Adverse events will be coded using the MedDRA dictionary (version 24) and summarised at the preferred term level. Severity (mild / moderate / severe),

seriousness (Yes / No) and relationship to study treatment (Unrelated / Unlikely to be related / Possibly related / Probably related / Definitely related) will also be collected.

An adverse event of the same type (i.e. same preferred term) will be counted as a separate occurrence if the start and end date of sequential events are separated by > 1 day.

Further detail on how adverse events will be summarised and reported is provided in section 6.

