10.2 Data Handling and Record Keeping

Overall responsibility for data collection lies with the Chief Investigator. Data collected on paper Case Report Forms will be entered onto a secure validated clinical data management system. A unique study identifier will be used to identify participants on case report forms. Data will be handled, computerised and stored in accordance with the Data Protection Act 2018 and the General Data Protection Regulation. The quality and retention of study data will be the responsibility of the Chief Investigator. All study data will be retained in accordance with the latest Directive on GCP (2005/28/EC) and local policy.

The CDMS (Sealed Envelope) used for this trial is fully compliant with all regulatory frameworks for research of this nature. It uses a secure web-based interface for data entry; no data are stored on computers at site. The system has an inbuilt back-up facility, through Sealed Envelope's hosting partner Rackspace's secure premises in London, and is managed and supported by the Rackspace team.

Where there is electronic storage of non-identifiable data it will be on a password protected device and/or database.

The study questionnaires will be completed at each study visit by the patient, with the assistance of the research team if required, directly onto paper with subsequent transcription to the eCRF by site staff. If visits are being carried out remotely, questionnaires can be completed over the phone or videoconference by the clinician and participant, before being transcribed to the eCRF by site staff.

Questionnaires can also be posted to the participant, from the site, for completion by the participant and return to the site.

The falls diaries will be returned by the participants at study visits with falls data entered into the eCRF by site staff. If participants forget their falls diaries, they will be provided with a new diary to complete from that visit onwards and pre-paid addressed envelopes will be provided during the visit to post their completed diary back to site staff to facilitate timely data entry.

If study visits are conducted remotely, the information from the falls diary can be collected over the phone or video call and the falls diary posted back to the site team. A replacement falls diary can be provided to the participant via post.

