5.2 Analysis of secondary outcomes

Activities of daily living (ADLs) measured by the Nottingham Extended ADL scale

Analysis Set 1 will be used for analysis. All available data will be reported according to randomised treatment allocation.

The NEADL score and change from baseline at each follow-up visit will be summarised descriptively by randomised treatment group. The number with data, mean, standard deviation, median and range will be reported, see Example Table 7.

Example Table 7: NEADL

NEADL score	V	/alue at follow-up v	isit	Change from baseline			
NEADL SCOLE	Control	Fludrocortisone	Midodrine	Control	Fludrocortisone	Midodrine	
Month 3							
N							
Mean (SD)							
Median (Range)							
Month 6							
Ν							
Mean (SD)							
Median (Range)							
Month 12							
N							
Mean (SD)							
Median (Range)							

Falls and syncope (number of falls, number of fallers/non-fallers, fall rate per person year, time to first fall, fall-related injuries, number of syncopal events)

Analysis Set 1 will be used for analysis. Data from all participants with at least one falls diary available will be reported according to their randomised treatment allocation.

The number of falls reported per participant will be tabulated as frequency and percentage and summarised as mean, SD, median and range. The total number of falls and total follow-up time from participants allocated to each randomised group will be reported. The simple, unadjusted incidence rate (IR) of falls per person year (i.e. total number of falls / total follow-up time) will be calculated in each randomised treatment group and presented with 95% CIs.

The same approach as above will be used for reporting of syncopal events, and a combined outcome of falls and syncopal events.

The number of fallers (i.e. the number of participants reporting at least one fall over the 12 month period) will be reported as frequency and percentage out of those returning at least one fall diary.

Time to first fall will be calculated and tabulated by whether this was within the first 3 months from randomisation, between 3 and 6 month follow-up or after 6 month follow-up.

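### Fall and syncope rates count undiaried months before the last diary as observed time, and the 12-month faller percentage makes no allowance for incomplete diaries

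*SAP*

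**What the plan says.** Under SAP section 2.4.2, falls and faints are self-reported and "collected in monthly falls diaries which should be returned at three, six and 12 month follow up time points".

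- **Numerator:** "The number of falls for each participant will be summed over the 12 month period".
- **Denominator:** each participant's "observation time will be measured as the time (in years) from randomisation to the date of the last completed fall diary".
- **Syncope:** "The syncopal event rate will be calculated as described above". A combined fall and faint rate is also reported.
- **Non-faller:** a participant is "a non-faller if they did not report a fall and returned at least one fall diary". SAP section 5.2 then has fallers over 12 months "reported as frequency and percentage out of those returning at least one fall diary".

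No minimum diary coverage and no rule for gaps is given. SAP section 5.4 plans no imputation outside questionnaire scoring. Example Table 8 puts time to first fall in three bands, with no count of those still observed in each.

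On forgotten diaries, Protocol section 10.2 says: "If participants forget their falls diaries, they will be provided with a new diary to complete from that visit onwards". It also provides pre-paid envelopes for sending the completed diary back. Protocol section 5.4.2 allows diary data to be taken by telephone.

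**The concern.** A rate needs a denominator that holds only the time in which an event could have been recorded. Here the denominator is calendar time up to the last diary. Suppose a participant forgets the diary at month 6, never posts it, and returns the next one at month 12. Months 4 to 6 then count as observed, although no fall in them could reach the numerator.

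The faller percentage has a separate and wider problem. It is presented as a 12-month proportion, but someone with one fall-free month carries the same weight as someone with twelve. Stopping early is enough to cause this; no gap is needed.

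Other data will not fill the hole. Protocol section 7.3 exempts falls from adverse event recording unless related or serious, although resulting injuries are recorded. Falls without injury therefore depend on diaries. The rates are to be reported with 95% confidence intervals, which do not reflect overcounted person-time. The trial is open-label, so diary completeness could differ by arm.

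**Working it through.** The documents state no fall rate, faller percentage or diary return figure, so there is no plan figure to reproduce. Return probabilities, gap lengths and fall rates below are assumptions. The diary unit (monthly), the return points (3, 6 and 12 months) and the two definitions come from SAP section 2.4.2.

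**Rate.** If falls occur equally often in recorded and unrecorded months, reported rate / true rate = months covered by diaries / months credited.

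*One participant*
- Diaries for months 1–3 and 7–12: 9/12 = 0.75.
- Diaries for months 1–3 and 12 only: 4/12 = 0.33.
- Diaries for months 1–3, then none: 3/3 = 1.00. Early stopping causes no bias here.

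*A whole arm, batches lost independently.* Batches cover 3, 3 and 6 months. Each is returned with probability p, and q = 1 − p. Expected covered months are 12p. Expected credited months are 12p + 6qp + 3q²p. The ratio is 12 / (12 + 6q + 3q²).

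*A whole arm, monthly diaries lost independently.* Covered months are 12p. Credited months are 12 − (q/p)(1 − q¹²).

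| Return probability | Batch loss | Monthly loss |
|---|---|---|
| 0.9 | 12/12.63 = 0.950 | 10.8/11.889 = 0.908 |
| 0.8 | 12/13.32 = 0.901 | 9.6/11.75 = 0.817 |
| 0.7 | 12/14.07 = 0.853 | 8.4/11.571 = 0.726 |
| 0.6 | 12/14.88 = 0.806 | 7.2/11.333 = 0.635 |

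*A whole arm, fixed share s with one gap of g months, everyone else complete.* The ratio is (12 − s·g)/12:
- 10% with 1 month missing: 11.9/12 = 0.99.
- 20% with 3 months missing: 11.4/12 = 0.95.
- 30% with 6 months missing: 10.2/12 = 0.85.

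**Faller percentage.** At λ falls per person-year (Poisson), the chance of at least one recorded fall in m months is 1 − exp(−λm/12). With λ = 1, twelve months give 63.2% and three months give 22.1%.
- 15% of participants with only three months: 0.85 × 63.2% + 0.15 × 22.1% = 57.0%.
- 30% with only three months: 0.70 × 63.2% + 0.30 × 22.1% = 50.9%.

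| Assumed falls per person-year | True 12-month risk | 15% with 3 months only | 30% with 3 months only |
|---|---|---|---|
| 0.5 | 39.3% | 35.2% | 31.1% |
| 1 | 63.2% | 57.0% | 50.9% |
| 2 | 86.5% | 79.4% | 72.3% |

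The 15% share equals the attrition assumed in the sample size (SAP section 2.6). It is used only as a plausible value; the plan does not predict it for diaries.

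**The case against.** The strongest reply is that the rate rule does what is needed for the commonest loss. When diaries stop, person-time stops too, so only gaps before the last diary matter. The protocol also has a recovery route: a forgotten diary can be posted in a pre-paid envelope or its contents taken by telephone. That passage describes how gaps are closed, and is not evidence that they are common. These points stand. The recovery route narrows gaps but does not ensure there are none.

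A reader might infer that all rates and faller percentages are certain to be too low. The documents do not support that. Without intermediate gaps the rate is unaffected. If a diary is missing because nothing happened, crediting that time is right. The error can even reverse. If falls reported by telephone after the last completed diary enter the 12-month numerator, time is short relative to events. For example, if 15% have a last diary at month 6 but falls counted to month 12, the rate is 12/(0.85 × 12 + 0.15 × 6) = 1.08 times the truth.

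A reader might also infer a distorted comparison between arms. Return of 90% in one arm and 70% in the other would turn equal rates into a ratio of 0.853/0.950 = 0.90 (batch loss) or 0.726/0.908 = 0.80 (monthly loss). No rate ratio is now planned, however: ratios appear only in the Appendix, for the full trial that did not happen. Similar gaps in all arms would largely cancel in any case.

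Finally, SAP section 4.1.3 tabulates availability of outcome data by visit and arm, and total follow-up time is shown in Example Table 8. This should make much uneven completeness visible, but it corrects neither denominator.

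**Conclusion.** The point holds in conditional form. As written, the SAP credits undiaried months before the last completed diary, and nothing elsewhere in the descriptive plan corrects this. The fall, syncope and combined rates are understated if such gaps exist and events occur in them. Under the assumed return of 90% to 60%, the rate is 95% to 81% of the truth with batch loss and 91% to 64% with monthly loss. Since diaries are handed back in batches, the smaller bias is the more natural expectation. With no intermediate gaps it is zero.

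The faller percentage, read as a 12-month proportion, is the more exposed measure, because early stopping lowers it too. It reads 57% instead of 63% at an assumed 1 fall per person-year with 15% having only three months of diaries.

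Confidence is high on the wording and low on the size, since gap frequency and fall rate are not in the documents. Severity is minor to moderate: recruitment closed during the pilot, no tests are planned, and these are descriptive secondary outcomes.

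**What to change.** In SAP section 2.4.2:

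1. Define observation time as the sum of months actually covered by completed diaries, including months whose content was collected by telephone.
2. Count only falls and faints that occurred in those months.
3. State that syncope and the combined outcome use the same person-time.

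In section 5.2 and Example Table 8:

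4. Report diary coverage by arm (months covered out of months due).
5. Either show the faller percentage beside a Kaplan-Meier estimate of first fall, which the Appendix already specifies for the full trial, or label it as unadjusted for incomplete diaries.

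If Kaplan-Meier is used, the censoring rule must be written down. Censoring at the end of continuous coverage would remove anyone missing the first diary and discard first falls reported after a gap. With so few participants, the label plus the coverage table may be the better choice.

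The cost is SAP wording, a small change to the derivation program and slightly smaller person-years. No new data collection is needed, provided the database records which months each diary or telephone report covers; the documents do not confirm this.
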